Studies have compared single- with dual-task performance on COP post-concussion, (Degani et al., 2017) or the presence of saccadic dysfunction post-concussion, using visually-based cognitive dual-tasks (Rizzo et al., 2016; Subotic et al., 2017). However, to date, no study has directly compared the effect BNO as an intervention on measures of COP velocity, objective metrics of saccadic eye movement, and symptoms during the performance of single- and visually-based cognitive dual-task balance conditions in a concussion population. This makes it difficult for clinicians to make evidence-informed choices in the management of individuals who experience persistent balance deficits beyond the expected period of normal recovery following a concussion. This study aims to address this gap by assessing the efficacy of a BNO intervention trial in adults with persistent post-concussion balance problems compared with a control condition using both single and visually-based cognitive dual-task balance paradigms. The study is designed as a randomized controlled crossover test with a sample size calculated a priori to ensure the contribution of high quality evidence to a nascent body of literature.

OBJECTIVES

Purpose

The overarching research question is the following: What is the effect of BNO compared with no binasal occlusion on measures of static balance, saccadic eye movement functions, and symptoms in adults who continue to experience dizziness one month or longer following a concussion? The specific objectives of this study are (1) to measure the effect of BNO on postural sway, compared with non-occluded vision during quiet stance on a force plate; (2) to examine the impact of BNO on postural sway while performing a visually based cognitive dual-task compared with target-focused vision, as measured during quiet stance on a force plate; (3) to compare the effect of BNO on saccadic eye function, compared with non-occluded vision during a timed reading task. Saccadic eye function will be quantified as time to completion during the KDT and the total number of saccades; (4) to determine the relationship between a rapid number naming task and observable saccadic eye function; (5) measure the association between self-reported symptoms, disability, and objective measures of balance in adults who continue to experience dizziness longer than one month after concussion.

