It is hypothesized that BNO will improve postural sway during a visually based cognitive dual-task more than during quiet stance. We also hypothesize that time to completion of a timed reading task will correlate positively with saccadic eye function, and that both will show improvement with BNO. It is further hypothesized that perceived disability due to dizziness and neck pain would be greater in

individuals with increased postural sway. This article presents the research protocol for this study.

METHODS

Design

This cross-sectional study will examine the effect of BNO on balance in adults aged 18-65 years who continue to experience symptoms one month or more following a concussion. A 2-task, 2-period, 2 treatment condition randomized crossover study design will be used in order to be balanced with respect to first-order effects, as each condition will precede the other condition only once. Potential participants will be screened for eligibility during a telephone interview. Following enrollment, they will be randomized to one of two condition sequences and act as their own control group. Participants will perform two different balance tasks repeated under both treatment (BNO) and control (no BNO) conditions. The treatment/control conditions will be the same for each participant with only the order of each treatment/control sequence randomized. Post-concussion syndrome is considered chronic and stable, and thus suitable for a crossover study design. Likewise, the application of BNO is intended to improve immediate functional balance and saccadic eye movement, rather than cure the concussion. No evidence of the effect time of BNO has been reported in the literature. Based on clinical experience of two of the authors, the treatment effect is limited to the time of application, so there should be no carryover effect between conditions and a negligible washout period between trials is considered sufficient. To minimize any risk of potential carryover effects, patients will also be asked to wait the greater of 1 minute, or until all symptoms return to their pre-test baseline before performing the subsequent task. A summary of the study design is available in Figure 1. All study procedures will be conducted at one of two private rehabilitation clinics in Ottawa, Canada.

Participants

Patient selection

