Participants will be randomly assigned to one of two groups for a crossover study design. Each group will complete both arms of the study, randomized to sequence, starting with either the control condition or the intervention condition. The intervention condition consists of performing the identical balance tasks while wearing glasses overlaid with BNO. Researchers performing the intervention will not be blinded to group allocation due to the crossover design.

OUTCOME MEASURES

For each arm of the study, participants will complete two trials of static balance while standing on a force plate that will record movement of the center of pressure (COP) under their feet. Sensors from an electromagnetic tracking system will also be attached to each participant at the base of the skull, T5, and L5 along the spine, collecting acceleration of movements, angular velocity of movements, and angular rotation of the earth. The sensors will record accelerations of movements, angular velocities, and angular rotations. Throughout each trial condition, Tobii™ eye tracker glasses will be worn to measure and record saccadic eye movements and time to task completion.

Primary outcome

Balance – COP

Measurement of postural sway as an indicator of persistent balance impairment post-concussion builds upon previous studies demonstrating increased postural sway in the acute period following a concussion (Goble et al., 2016). The primary outcome of interest is the mean M/L and A/P velocity of COP, in addition to the 95% ellipse during different conditions of static balance. The minimal clinical difference

considered to demonstrate a change in postural sway is 5cm based on a previous validation study in a concussed population (Goble et al., 2016).

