A force to the head or body that results in a concussion is of sufficient force to injure the soft tissue and joints of the cervical spine. Altered proprioception from injured cervical spine structures can contribute to symptoms of dizziness commonly associated with concussion. The NDI is the most commonly used self-report outcome measure for neck pain (MacDermid et al., 2009). The index is a simple and quickly administered 10-item questionnaire measured on a 6-point Likert scale from 0=no disability to 5 = full disability. Scores range from 0-50, with 50 representing the highest level of disability. Psychometric properties of scores demonstrate highly stable test-retest reliability (r=0.94-0.95) in patients with neck pain longer than 3 weeks (MacDermid et al., 2009). Clinically important difference have been reported with a 5-7 point change in score depending on whether the pain was of musculoskeletal or neural origin (MacDermid et al., 2009).

Saccadic eye function

Saccadic eye function will be assessed with two measures, a Tobii[™] Pro wearable eye tracker and the KDT. Tobii[™] Pro wearable eye tracker uses infrared videooculography to analyze patterns of eye movement in terms of fixations and saccades (www.tobiipro.com). Longer, more complicated visual tasks, such as rapid number naming, require longer processing times. The number of saccades completed during each balance condition will be recorded by the Tobii[™] Pro. The KDT is a vision-based test of rapid number naming speed that acts as a proxy measure for saccadic eye movement (Galetta, Liu, et al., 2015). The KDT consists of a demonstration card, plus a series of 3 increasingly more difficult test cards of variably spaced single digit numbers (Subotic et al., 2017). Following completion of the demonstration card, participants are asked to read each test card from left to right, top to bottom, as quickly as possible without errors. A summary score of the test is recorded as the total time to complete all 3 test cards, measured in seconds. Time to completion for the KDT will be recorded by the TobiiTM Pro. A meta-analysis demonstrated high test-retest reliability (ICC=0.92; CI_{95%}: 0.91, 0.94) in baseline trials (Galetta, Liu, et al., 2015).

Domain	Measure	Outcome of Interest		
		Baseline Disability	Primary	Secondary
Cervical spine	Neck Disability Index	Х		
Dizziness	Dizziness Handicap Inventory	Х		
Postural sway	M/L COP excursion		Х	
	A/P COP excursion		Х	
	95% ellipse COP		Х	

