Eye tracking	Saccades			Х
	King Devick Test			X
Symptoms	Post- Concussion Symptom Scale			X

 Table 2: Outcome measures

(*M*/*L*=medial/lateral; *A*/*P*= anterior/posterior; COP,=centre of pressure)

Interventions

Balance Testing Protocol

All participants will be asked to perform a repeated measure of 2 different balance tasks under 2 different treatment conditions as outlined below. Each trial of balance will take 2 min to administer, and will be performed with the participant wearing socks. Before and after each trial, participants will be asked to rate if they are experiencing any headache, dizziness, nausea, or fogginess on a scale of 0 to 10. Following each trial, a washout period will be given as the greater of a minimum of 1 minute of rest or until symptoms aggravated by the task return to their pretrial baseline. A time period of two minutes was chosen as a sufficient interval over which to collect stable COP data according to the International Society for Posture and Gait Research (Scoppa, Capra, Gallamini, & Shiffer, 2013), while aligning with time required to complete the KDT.

For balance task A, participants will be asked to stand with their feet shoulder width apart on the BTS with their hands placed on their hips. They will be asked to hold this position for two minutes with their eyes open, vision fixed on a small target (dot), and to focus on standing as still as possible.

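### The saccade count is not tied to the interval of the timed KDT reading; if it is taken over the 2-minute trial, it carries reading speed

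*Protocol*

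**What the plan says.** **Objectives (Purpose).** The third objective is "to compare the effect of BNO on saccadic eye function, compared with non-occluded vision during a timed reading task". It adds: "Saccadic eye function will be quantified as time to completion during the KDT and the total number of saccades". The fourth objective is the relation between rapid number naming and observed saccadic function. The hypotheses expect that "time to completion of a timed reading task will correlate positively with saccadic eye function", and that both will improve with binasal occlusion (BNO).

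**KDT time (Saccadic eye function).** "A summary score of the test is recorded as the total time to complete all 3 test cards, measured in seconds". This is one reading.

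**Saccade count (same section).** "The number of saccades completed during each balance condition will be recorded by the" eye tracker. The Outcome Measures section similarly says that the glasses "will be worn to measure and record saccadic eye movements and time to task completion".

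**Trial length (Balance Testing Protocol).** "Each trial of balance will take 2 min to administer". In task B the KDT is said usually to take under two minutes. Participants who finish early start again and read until the period ends. Those who need longer read on to completion, and only the centre-of-pressure (COP) recording is given a 2-minute stop. An error also leads to a restart.

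**Planned statistical analyses.** A Wilcoxon signed rank test compares the number of saccades made on the KDT between conditions, with no start or stop given for the count.

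**The concern.** Time and count are the two halves of one construct in objective 3, and they are related to each other in objective 4. They should therefore cover the same stretch of reading. Time covers one reading. The only explicit window for the count is a whole trial, which usually holds more than one reading. A count over a fixed window is a rate, and faster reading raises it even when nothing about the saccades in a reading has changed.

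Three things are at stake: what the Wilcoxon test on saccades measures, what the time–saccade relation (a planned publication topic) means, and whether two analysts following the same text would produce the same variable. For readers who need more than 2 minutes the quantity changes again. If the tracker runs to completion, their count is one reading, so rates and per-reading counts can enter the same paired test.

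**Working it through.** The protocol gives no figure for saccades, so there is none to reproduce. The 120 s trial, n = 40 and two-sided alpha 0.05 come from the protocol. Every other input below is assumed.

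**1. What the whole-trial count measures.** Let T be the time for one reading and S the saccades in it. At a constant saccade rate:
- T < 120 s: count = S × 120/T.
- T > 120 s, tracker run to completion: count = S. If it were stopped at 120 s, the count would be S × 120/T. For example, S = 100 and T = 150 s gives 100 or 80.

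**2. Effect on the BNO contrast (T < 120 s in both conditions).** If time falls by a fraction dt and saccades per reading by ds, the whole-trial count changes by (1 − ds)/(1 − dt) − 1.

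| Time | Saccades per reading | Whole-trial count |
|---|---|---|
| −5% | 0 | 1/0.95 − 1 = +5.3% |
| 0 | −10% | −10% |
| −3% | −5% | 0.95/0.97 − 1 = −2.1% |
| −5% | −10% | 0.90/0.95 − 1 = −5.3% |
| −5% | −5% | 0 |
| −10% | −5% | 0.95/0.90 − 1 = +5.6% |

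A fall in S is kept if time is unchanged, shrunk if time falls proportionally less, cancelled if it falls equally, and reversed only if time falls proportionally more. A participant crossing 2 minutes (125 s to 112.5 s, S down 5%) shows 0.95 × 120/112.5 − 1 = +1.3%.

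**3. Effect on the Wilcoxon test.** Simulation of 40 pairs: baseline T and S log-normal and independent, CV 20%, mean S 150, SD of within-person log ratios 0.10. Here r is the correlation between the log ratios of time and saccades.

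*Mean T 60 s; entries are the chance of a significant fall unless marked.*

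| Time / saccades per reading | Per reading | Whole trial, r = 0 to 0.5 | Whole trial, r = 0.7 |
|---|---|---|---|
| −5% / 0 (significant rise) | about 3% | about 65–89% | about 98% |
| 0 / −5% | about 83% | about 50–83% | about 97% |
| −3% / −5% | about 83% | 10–20% | about 32% |
| −5% / −10% | 100% | about 54–87% | about 98% |
| −10% / −5% (significant rise) | 0% | about 70–92% | about 99% |

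If mean T is 120 s, the last row's rise falls to about 21–36% for r from 0 to 0.5, and the first row's to about 49–72%.

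The second row can gain power because, with equal SDs s, the log whole-trial ratio has variance 2s²(1 − r). This is below s² once r exceeds 0.5.

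**4. Effect on the time–saccade relation (T < 120 s).** On the log scale, with SDs σT and σS and correlation ρ, covariance(time, count) = ρσSσT − σT². It is always lower than for the per-reading count, and negative when ρσS < σT. Take ρ = 0.5 and σS = 0.20:
- σT = 0.05: (0.10 − 0.05)/√0.0325 = +0.28.
- σT = 0.15: (0.10 − 0.15)/√0.0325 = −0.28.

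Over 108 assumed scenarios (mean T 60–120 s, time CV 5–25%, saccade CV 10–30%, latent correlation 0.3–0.7), the Spearman correlation with time ran from +0.28 to +0.69 per reading and from −0.92 to +0.63 for the whole trial. It was lower in all 108.

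**5. Restarts after an error.** The protocol does not say whether an abandoned attempt enters the time or the count. One abandoned half-way would add 50% to that participant's KDT time if counted. If it entered one measure and not the other, the intervals would differ again.

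**The case against.** The strongest reply is that the protocol never adopts the 2-minute count for its analysis. The sentence about the balance condition covers both tasks, including the one where participants fixate a dot, and it can be read as saying only what the tracker captures. The analysis section speaks of saccades made on the KDT, and objective 3 of a timed reading task. Elsewhere the protocol treats completing the KDT as one reading, so a single reading is a natural interpretation. Segmenting a recording is often left to the analysis plan, and the raw recording would allow either count later.

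Much of this stands. A reader might infer that the protocol has fixed a wrong saccade variable, and the text does not support that. What remains is that re-readings are also KDT readings, neither phrase gives a start or stop, and the protocol itself states a window and a re-reading procedure that together lead away from the timed interval. What an outcome counts is protocol content, and it is better settled before results are seen.

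Two further objections also stand. The protocol does not say that fewer saccades is the improvement; that is an inference. And loss of power is not general: with a high time–saccade correlation and little change in time, the whole-trial count can have more power. The 60 s mean is also only an assumption, since the protocol says the 2-minute trial was chosen partly to match the time the KDT needs.

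**Conclusion.** The point holds as a cheap improvement to one secondary outcome and objective 4. The count is not put on the interval of KDT time. If the only explicit window is followed, it becomes S × 120/T for readers under 2 minutes and so mixes reading speed into the saccade comparison. The arithmetic rests on a constant saccade rate within a trial. With S unchanged, 5% faster reading gives +5.3%, and the correlation with time is shifted downward.

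The practical size cannot be fixed from the document, because mean KDT time, its variability and the time–saccade correlation are not given. A reader might infer that the saccade result will be reversed, or that power will be lost as a rule. Neither follows: reversal needs time to fall proportionally more than saccades per reading, and power can move either way. Nor does the choice of count window touch the primary COP outcome or the paired test of KDT time.

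**What to change.** In the Saccadic eye function section, the task B description and the planned analyses, define the saccade count used in the Wilcoxon test and in the time–saccade analysis over the same interval as the recorded KDT time in each task B trial. Segment it from the eye-tracker recording already planned. State that later re-readings serve only to fill the COP recording. State one rule for attempts restarted after an error and apply it to both time and count; which rule is chosen matters less here than that both measures follow it.

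Testing instructions, visits and data collection do not change. The cost is a wording change and some segmentation work, and saccades made during re-readings are not used.

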For balance task B, participants will be asked to stand shoulder width apart on the BTS with their hands on their hips. Participants will be asked to complete a cognitive task while they maintain their balance. The visually based cognitive dual-task will involve the participants performing the King-Devick Test (KDT). Test cards will be fixed to a wall and positioned 12 inches from the participant's face at eye level. Participants will be asked to read the numbers out loud as quickly and as accurately as possible, from left to right, beginning at the top left corner of each test card. The total time to read all 3 test cards and the total number of errors committed will be recorded. If a participant makes an error, they will be asked to restart the test. The test usually takes less than two minutes to complete. Participants who complete the KDT in less than 2 minutes will be asked to restart the test from the beginning and continue reading for the remainder of the test period. Those individuals who require more than the allotted 2 minutes to complete the KDT will continue with the rapid number naming task until completion, and COP data will stop being collected at 2 min.

Throughout each trial, participants will be fitted with a pair of Tobii™ eye tracking glasses that will record their eye movements.

Control condition: normal vision

During the control arm of the trials, the eye tracking glasses will remain unobstructed and vision will not be occluded.

Experimental intervention: BNO

During the intervention arm of the trials, strips of occlusive material will be placed on the medial portion of each lens of the Tobii[™] eye tracking glasses to occlude central integrated vision.

Planned statistical analyses

Baseline characteristics for participants will be compared with descriptive statistics (mean, SD, n, %).

The primary objective, the effect of BNO on postural sway, will be addressed by using a dependent t-test to compare differences between treatment conditions for each COP variable. A similar analysis using a dependent t-test (group^xKDT_{time to} completion) will be performed to assess the secondary objective, the effect of BNO on reading. Additionally, a Wilcoxon Signed Rank test will be used to determine if there is a significant difference in the number of saccades completed on the KDT between

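### The restart-on-error rule leaves King-Devick (KDT) time undefined once an error occurs, and the saccade count has two windows, so objectives 3 and 4 depend on choices the protocol does not make

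*Protocol*

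**What the plan says.** The Balance Testing Protocol section (balance task B) sets out the recording: "The total time to read all 3 test cards and the total number of errors committed will be recorded". The next sentence adds the restart rule: "If a participant makes an error, they will be asked to restart the test". Two further rules cover the 2-minute trial. For early finishers: "Participants who complete the KDT in less than 2 minutes will be asked to restart the test from the beginning", after which they read until the period ends. For slow finishers: "Those individuals who require more than the allotted 2 minutes to complete the KDT will continue with the rapid number naming task until completion", while centre-of-pressure (COP) collection stops at 2 minutes.

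The Saccadic eye function section defines the score: "A summary score of the test is recorded as the total time to complete all 3 test cards, measured in seconds". It does not mention failed attempts. On the eye tracker it says: "The number of saccades completed during each balance condition will be recorded by the Tobii". Planned statistical analyses instead describes a Wilcoxon test for "a significant difference in the number of saccades completed on the KDT between" the two conditions, and a dependent t-test for KDT time.

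Objective 3 compares KDT time and saccades with and without binasal occlusion (BNO). Objective 4 is "to determine the relationship between a rapid number naming task and observable saccadic eye function", and the stated hypothesis is a positive correlation. Table 2 lists saccades and the KDT as secondary outcomes.

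**The concern.** When a participant errs, the protocol does not say what the clock does, and both possibilities cause trouble.

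- **Clock runs on.** KDT time includes every abandoned attempt. A BNO effect on accuracy alone would then appear as a time effect. Chance restarts would also add noise to each paired difference, which weakens the t-test for objective 3.
- **Clock resets.** The scored pass is read on cards just rehearsed, but only by those who erred. If BNO changes how often people err, the amount of rehearsal differs between conditions.

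Objective 4 adds a second undefined quantity. A saccade count per balance condition suggests the fixed 2-minute trial. A count on the KDT suggests start to completion. The two windows respond to restarts and to reading speed in different ways, so the correlation with KDT time can change sign with the choice.

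This goes beyond detail that an analysis plan could supply later. A participant who was stopped and sent back has no uninterrupted first reading for any analysis to use.

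**Working it through.** **What can be reproduced.** The protocol states no KDT effect size, standard deviation, error rate or saccade count, so there is no KDT figure to reproduce. The sample size of 40 rests on COP excursion and is not at issue. It is used here only as the number of pairs.

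**Inputs.** From the protocol: 40 pairs, two-sided alpha 0.05, dependent t-test, restart at any error, KDT time not capped at 2 minutes. Assumed:
- clean pass of mean 60 s, SD 12 s;
- saccades per clean pass of mean 150, SD 22, independent of time (true correlation zero);
- SD of the paired difference in clean-pass time 4.8 s;
- errors at a constant rate along a pass, with L expected errors per full pass;
- the whole test restarts, with no limit on restarts.

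**Step 1: mean recorded time, running clock.** Expected time to an error-free pass of length T is T × (e^L − 1)/L.
- L = 0.10: 60 × 1.052 = 63.1 s
- L = 0.25: 60 × 1.136 = 68.2 s
- L = 0.50: 60 × 1.297 = 77.8 s

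The chance of at least one restart is 1 − e^(−L), which is 0.10, 0.22 and 0.39.

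**Step 2: objective 3, running clock** (4,000 simulated trials of 40 pairs; variance share from 200,000 simulated participants).

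| L | Share of time variance due to reading speed | SD of paired difference | Power for a true 3 s gain | Mean shift if BNO only halves errors | Rejection rate in that case |
|---|---|---|---|---|---|
| 0 | 1.00 | 4.8 s | 97% | 0 s | 5% |
| 0.10 | 0.54 | 16.3 s | 26% | −1.6 s | 7% |
| 0.25 | 0.32 | 27.5 s | 12% | −4.2 s | 18% |
| 0.50 | 0.19 | 44.4 s | 9% | −9.8 s | 35% |

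The shift agrees with the formula. At L = 0.25 halved to 0.125, (e^0.125 − 1)/0.125 = 1.065, and 60 × (1.136 − 1.065) is about 4.3 s.

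**Step 3: objective 3, clock reset.** The score is the clean-pass time and power stays at about 97%, provided practice from failed attempts is ignored. The documents give nothing from which to size that practice effect.

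**Step 4: objective 4, Spearman rho when the truth is zero** (200,000 simulated participants). Counted to completion, time and saccades are multiplied by the same restart factor. Over 2 minutes, the count is taken as 120 × saccades per pass / seconds per pass.

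| L | Running clock, count to completion | Running clock, 2-minute count | Reset clock, final-pass count | Reset clock, 2-minute count |
|---|---|---|---|---|
| 0.10 | 0.18 | −0.71 | 0.00 | −0.79 |
| 0.25 | 0.38 | −0.61 | 0.00 | −0.79 |
| 0.50 | 0.61 | −0.49 | 0.00 | −0.79 |

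The 2-minute count gives a negative value even with no errors (−0.79 at L = 0), because slower readers complete fewer passes in a fixed time. Removing the restart rule alone therefore does not repair objective 4. With a between-person spread of about 17% for both time and saccades, the no-restart value is about −0.69.

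**The case against.** **The clock may reset.** Participants are asked to read without errors and the score covers all three cards, which fits an error-free pass timed from its own start. A reader might infer that the rule necessarily makes KDT time a mix of speed and restarts. The text does not settle that, so the point has to stay conditional. The reset reading is not clean either. It is true that everyone reads the same cards again under the second condition, but randomizing sequence balances that practice. It does not balance practice that depends on having erred.

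**The positive correlation is not simply built in.** A reader might infer that the restart rule guarantees support for the objective 4 hypothesis. That needs a running clock and a count to completion together. The eye-tracker sentence allows a 2-minute count, which pushes the other way.

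**Recording time and errors is not a contradiction.** Total time and total errors over all attempts can both be recorded. What is missing is the clock rule. Under the restart rule the error total is a restart count, which is still usable, although no planned analysis uses it.

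**A smaller repair exists.** Stating a reset clock and counting saccades on the error-free pass also brings the induced correlation to about zero and keeps the restart rule's check on speed bought at the expense of accuracy. It leaves the rehearsal problem in place.

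**Unblinded staff.** The protocol says those performing the intervention are not blinded, and it names no one else to call errors. A misread digit is a fairly objective event, so little weight is placed on this.

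**The sizes are assumed.** This stands in full. At L = 0.10 the mean rises by only about 3 s.

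**Conclusion.** The point holds in conditional form. The protocol pairs a restart rule with a total-time score and does not say whether failed attempts count. It also gives two saccade windows.

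Under a running clock, objective 3 mixes speed with errors. On the stated assumptions, power for a 3 s gain falls from 97% to 26%, 12% and 9% at 0.10, 0.25 and 0.50 expected errors per pass. Under a reset clock the contamination is selective rehearsal, of unknown size. For objective 4 the artefact is positive under one combination of readings and negative under a 2-minute count, so even the sign of the result depends on an unstated choice.

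The direction of each effect follows from the rules as written. The magnitudes rest entirely on assumed error rates, times and saccade counts. The outcomes concerned are secondary, and nothing here shows that the primary COP comparison is affected. This is an inexpensive improvement worth making, because data collected under the restart rule cannot be repaired afterwards.

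**What to change.** In balance task B:
- Delete the restart-on-error sentence and have participants read on after an error.
- Define KDT time as the first complete reading of the three cards.
- Count saccades over that same reading, and use the same wording in the Saccadic eye function and Planned statistical analyses sections.
- Report the errors in that reading separately.
- Keep re-reading after completion only as filler for the rest of the 2-minute COP trial.
- For objective 4, name the saccade count alone as the measure of saccadic function, since objective 3 counts KDT time itself under that term.

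With time and saccades taken over the same single reading, the simulated correlation is about 0.00 when the truth is zero, and the recorded time no longer contains restarts.

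The cost is a few sentences of testing script, best changed before the first participant is tested. The downside is that the scored time may contain errors, so it must be read alongside the error count. If the restart rule is kept, the minimum is to state the clock rule, fix one saccade window on the scored pass, and report restarts as an outcome, accepting the rehearsal effect.
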